8.3 AEs and SAEs

Adverse events will be reported by the participant (or, when appropriate, by a caregiver, surrogate, or the participant's legally authorized representative).

The study participant will be given the opportunity to report AEs spontaneously. A general prompt will also be given at each study visit to detect AEs. For example:

“Did you notice anything unusual about your health (since your last visit)?”

In addition, the Investigator should review any self-assessment procedures (eg, diary cards) employed in the study for potential AEs.

The Investigator and any designees are responsible for detecting, documenting, and recording events that meet the definition of an AE or SAE and remain responsible for following up AEs that are serious, considered related to the study treatment or study procedures, or that caused the participant to discontinue the study treatment (see Section 7).

New or worsening manifestations of SLE should be recorded as AEs only if they are assessed as serious.

All efforts should be taken to clarify the origin of the AE. This may require at any time point additional assessments including but not limited to additional laboratory assessments, imaging methods, EMGs and ECGs as medically indicated. Special caution should be taken on signs and symptoms of severe infections such as COVID-19.

For results disclosure on public registries (eg, ClinicalTrials.gov), TEAEs and treatment-emergent SAEs will be published.

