Events Meeting the AE Definition

• Any abnormal laboratory test results (hematology, clinical chemistry, or urinalysis) not related to SLE or other safety assessments (eg, ECG, radiological scans, vital signs measurements not related to SLE, including those that worsen from baseline, considered clinically significant in the medical and scientific judgment of the Investigator (ie, not related to progression of underlying disease).• Exacerbation of a chronic or intermittent pre-existing condition other than SLE including either an increase in frequency and/or intensity of the condition.• New conditions not SLE related detected or diagnosed after study medication administration even though it may have been present before the start of the study.• Signs, symptoms, or the clinical sequelae of a suspected drug-drug interaction.• Signs, symptoms, or the clinical sequelae of a suspected overdose of either study medication or a concomitant medication. Overdose per se will not be reported as an AE/SAE unless it is an intentional overdose taken with possible suicidal/self-harming intent. Such overdoses should be reported regardless of sequelae.• "Lack of efficacy" or "failure of expected pharmacological action" per se will not be reported as an AE or SAE. Such instances will be captured in the efficacy assessments. However, the signs, symptoms, and/or clinical sequelae resulting from lack of efficacy will be reported as SAE if they fulfil the definition of a SAE.

Events NOT Meeting the AE Definition

- Any clinically significant abnormal laboratory findings or other abnormal safety assessments which are associated with the underlying disease (SLE) except it fulfills seriousness criteria.
- SLE or expected progression, signs, or symptoms of the SLE except they fulfill seriousness criteria.
- Medical or surgical procedure (eg, endoscopy, appendectomy): the condition that leads to the procedure is the AE.
- Situations in which an untoward medical occurrence did not occur (social and/or convenience admission to a hospital).
- Anticipated day-to-day fluctuations of pre-existing disease(s) or condition(s) present or detected at the start of the study that do not worsen.

This document cannot be used to support any marketing application and any extensions or variations thereof.
PUBLIC COPY

Definition of SAE

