If an event is not an AE per definition above, then it cannot be an SAE even if serious conditions are met (eg, hospitalization for signs/symptoms of the disease under study, death due to progression of disease).

An SAE is defined as any untoward medical occurrence that, at any dose:	
a. Results in death	
b. Is life-threatening	
The term 'life-threatening' in the definition of 'serious' refers to an event in which the participant was at risk of death at the time of the event. It does not refer to an event, which hypothetically might have caused death, if it were more severe.

c. Requires inpatient hospitalization or prolongation of existing hospitalization	
In general, hospitalization signifies that the participant has been detained (usually involving at least an overnight stay) at the hospital or emergency ward for observation and/or treatment that would not have been appropriate in the physician's office or outpatient setting. Complications that occur during hospitalization are AEs. If a complication prolongs hospitalization or fulfills any other serious criteria, the event is serious. When in doubt as to whether "hospitalization" occurred or was necessary, the AE should be considered serious.
 
Hospitalization for elective treatment of a pre-existing condition that did not worsen from baseline is not considered an AE.

d. Results in persistent disability/incapacity	
The term disability means a substantial disruption of a person's ability to conduct normal life functions.This definition is not intended to include experiences of relatively minor medical significance such as uncomplicated headache, nausea, vomiting, diarrhea, [REDACTED], and accidental trauma (eg, sprained ankle) which may interfere with or prevent everyday life functions but do not constitute a substantial disruption.
e. Is a congenital anomaly/birth defect	

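### The SAE definition gives SLE death and SLE hospitalization as examples of events that cannot be SAEs, against the protocol's own AE rules

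*Protocol*

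**What the plan says.** The lead sentence of the SAE definition in Protocol Section 10.3 (Appendix 3) reads: "If an event is not an AE per definition above, then it cannot be an SAE even if serious conditions are met". Its parenthesis then gives two examples: "hospitalization for signs/symptoms of the disease under study, death due to progression of disease".

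The AE rules that this sentence depends on say something different.

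- Section 10.3, list of events not meeting the AE definition: "SLE or expected progression, signs, or symptoms of the SLE except they fulfill seriousness criteria". A parallel bullet makes the same exception for abnormal laboratory and other safety findings linked to SLE.
- Section 8.3: "New or worsening manifestations of SLE should be recorded as AEs only if they are assessed as serious".
- Section 10.3, on lack of efficacy: "the signs, symptoms, and/or clinical sequelae resulting from lack of efficacy will be reported as SAE if they fulfil the definition of a SAE".
- Section 10.3, seriousness criteria: death is criterion a, and inpatient or prolonged hospitalization is criterion c.

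The appendix also names admissions that are not AEs. One is elective: "Hospitalization for elective treatment of a pre-existing condition that did not worsen from baseline is not considered an AE". Another is an admission for social or convenience reasons. Expected day-to-day fluctuation of an existing condition that does not worsen is likewise not an AE.

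**The concern.** Section 8.3.1 sends sites to Section 10.3 for 24-hour SAE reporting, so this is the operative definition. In an SLE trial the two examples describe the most important disease-related outcomes: a death from lupus, and an admission for a flare.

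A site that took the examples at face value would send no SAE report and make no causality assessment. No non-serious AE record would take its place, because Section 8.3 records SLE manifestations as AEs only when they are serious. The event would drop out of the serious-TEAE secondary endpoint and the SAP's serious and fatal TEAE tables. The loss would fall on events where attribution matters: the protocol has the IDMC look at neuropsychiatric BILAG data because events may be wrongly put down to SLE.

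**Working it through.** The plan states no figure on this point, and no rate, power or error calculation applies. The check tests each example against the AE rules, the seriousness criteria and the stated exclusions.

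1. **Death due to SLE progression.** It meets criterion a, so it is serious. The Section 10.3 exclusion for SLE progression does not reach serious events, so the death is an AE. An AE that results in death is an SAE. None of the exclusions (elective, social or convenience, non-worsening fluctuation) covers a death. The example conflicts without qualification.

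2. **Hospitalization for new or worsening SLE.** It meets criterion c. Section 8.3 and the Section 10.3 exception both make it an AE, and hence an SAE. The elective exclusion does not apply, because it requires that the condition has not worsened. The example conflicts.

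3. **Elective admission for SLE that has not worsened, or a social or convenience admission.** These are not AEs under Section 10.3, so they cannot be SAEs. Here the example is consistent. The hospitalization example is therefore too broad rather than always wrong. Limiting the conflict to new or worsening SLE is conservative: read literally, the exception would also cover an unplanned admission for persistent, unchanged SLE.

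4. **Count of examples.** There are 2. One conflicts in every case; one conflicts only when the admission is for new or worsening SLE.

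5. **Outputs that would lose an omitted event.** SAP Section 10.1 lists 31 numbered TEAE summaries. Those restricted to serious or fatal events are items 3 (serious TEAEs), 4 (serious TEAEs by relationship) and 28 (fatal TEAEs by relationship): 3 of 31. The all-TEAE summaries would lose the event too. Items 25 and 26 cover non-serious TEAEs and would not recover it.

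6. **Partial fallback.** The SELENA Flare Index records need for hospitalization. Protocol Table 1-2 schedules it after Baseline at Weeks 12, 24, 36 and 48 (V5, V8, V11, V14). The post-Baseline treatment-period visits are V3 to V14, which is 14 − 3 + 1 = 12. Coverage is 4 of 12 visits.

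**The case against.** The strongest reply is that the sentence defers to the correct rule. It applies only to events that are not AEs under the definition just above it, and that definition keeps serious SLE inside. For a serious SLE event the condition fails and the sentence excludes nothing, so what remains is a badly chosen illustration. Other text also favors reporting. Section 8.3.1 asks for any SAE whatever its cause, and criterion c says that where there is doubt whether hospitalization "occurred or was necessary, the AE should be considered serious". Section 8.3.8, on anticipated SAEs in SLE, has no readable body in the public copy. The Amendment 3 history records that wording on SAE reporting was added there, so sites may already hold clear instructions.

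There are also other routes by which an event could surface:

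- BILAG and SLEDAI-2K at every visit, and efficacy data sent to the IDMC;
- ongoing SAE review and reconciliation (Protocol Section 8.4);
- tabulation and listing of deaths (Protocol Section 9.4.1) and disposition tables (SAP Section 5.1);
- post-mortem findings, and central source review on request.

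Much of this stands as a limit on consequence. It does not remove the conflict. If the AE definition governs, the death example is simply false. The lack-of-efficacy rule gives no independent protection, since it refers back to the SAE definition whose opening sentence names these outcomes as excluded. A clear Section 8.3.8 would still leave contrary current text in Section 10.3. None of the fallbacks is a 24-hour SAE report with a causality assessment, and the documents do not say that the routine reconciliation would catch an SLE event that was never entered as an SAE.

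**Conclusion.** The concern holds and should be fixed. Of the two examples, one contradicts the AE rules outright and the other contradicts them for admissions due to new or worsening SLE. The conditional rule itself is sound.

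Confidence is high for the conflict in the text only. The documents give no rate of serious SLE events and no figure by arm, so neither the number of events affected nor any difference between arms can be estimated. Nothing shows that any site has under-reported. The stake is expedited reporting and the completeness of the serious-TEAE secondary endpoint; the primary and key secondary efficacy endpoints are not affected. The consequence assumes that a site follows the examples rather than the exceptions beside them, and that Section 8.3.8 does not already prevent this.

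**What to change.** Reconcile Section 8.3 with the AE and SAE definitions in Section 10.3. Either delete the two examples, or replace them with admissions that the protocol itself treats as non-AEs: elective treatment of an unworsened existing condition, or a social or convenience stay. Confirm that Section 8.3.8 and Table 8-4 say the same, and send sites a short clarification.

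Before database lock, check recorded SLE deaths and hospitalizations against SAE status and query any mismatch. If the database is already locked, disclose the conflicting text and the result of the check in the CSR.

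The cost is one parenthesis in the protocol, one site memo and one reconciliation query. The reported SAE count could rise, by an amount that the documents do not allow one to predict.

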10.4 Appendix 4: Contraceptive guidance and collection of pregnancy information

Definitions

Woman of Childbearing Potential (WOCBP)

A woman is considered fertile following menarche and until becoming post-menopausal unless permanently sterile (see below).

Women in the following categories **are not considered WOCBP**:

1. Premenarchal
2. Premenopausal female with 1 of the following:
 - Documented hysterectomy
 - Documented bilateral salpingectomy
 - Documented bilateral oophorectomy
3. Postmenopausal female
 - A postmenopausal state is defined as no menses for 12 months without an alternative medical cause. A high follicle stimulating hormone (FSH) level in the postmenopausal range may be used to confirm a postmenopausal state in women not using hormonal contraception or hormonal replacement therapy (HRT). However, in the absence of 12 months of amenorrhea, a single FSH measurement is insufficient.
 - Females on HRT and whose menopausal status is in doubt will be required to use one of the non-estrogen hormonal highly effective contraception methods if they wish to continue their HRT during the study. Otherwise, they must discontinue HRT to allow confirmation of postmenopausal status before study enrollment.

Contraception Guidance

Male participants

Male participants with female partners of childbearing potential (including partners who are pregnant or breastfeeding [including pumping breast milk to feed to a child]) must use contraception if any of the following criteria are met:

- Genotoxic study medication
- Study medication where reproductive toxicology studies have not yet been conducted
- Study medication with demonstrated or suspected human teratogenicity/fetotoxicity at subtherapeutic exposure levels if relevant systemic concentrations may be achieved in WOCBP from exposure to seminal fluid

Male participants with female partners of childbearing potential are eligible to participate if they agree to ONE of the following during the protocol-defined time frame in Section 5.1:

- Are abstinent from penile-vaginal intercourse as their usual and preferred lifestyle (abstinent on a long-term and persistent basis) and agree to remain abstinent.
- Agree to use a male condom plus partner use of a contraceptive method with a failure rate of <1% per year as described in the table below when having penile-vaginal intercourse with a WOCBP who is not currently pregnant.
- Agree to use a male condom when having penile-vaginal intercourse WOCBP who is currently pregnant.

In addition male participants must refrain from donating sperm for the duration of the study and for 17 weeks after the final dose of study medication.

Male participants with a pregnant or breastfeeding (including pumping breast milk to feed to a child) partner must agree to remain abstinent from penile-vaginal intercourse or use a male condom during each episode of penile penetration during the study and for at least 17 weeks after the final dose of study medication.

Female participants

Female participants of childbearing potential are eligible to participate if they agree to use a highly effective method of contraception consistently and correctly as described in the table below. If the Investigator considers another contraception method not listed below but is proven to have a failure rate <1/100 patient-years (PEARL index) or participants use a combination of contraceptives with a failure rate <1/100 patient-years, then this method may be considered as effective contraception after discussion with the Medical Monitor or Sponsor Study Physician.

Highly Effective Contraceptive Methods^a

Highly Effective Contraceptive Methods That Are User Dependent^b

Failure rate of <1% per year when used consistently and correctly.

Combined (estrogen and progestogen containing) hormonal contraception associated with inhibition of ovulation^c

- Oral
- Intravaginal
- Transdermal

Progestogen only hormonal contraception associated with inhibition of ovulation

- Oral
- Injectable

Highly Effective Methods That Are User Independent

Implantable progestogen only hormonal contraception associated with inhibition of ovulation

- Intrauterine device (IUD)
- Intrauterine hormone-releasing system (IUS)
- Bilateral tubal occlusion

Vasectomized partner

A vasectomized partner is a highly effective contraception method provided that the partner is the sole male sexual partner of the WOCBP and the absence of sperm has been confirmed. If not, an additional highly effective method of contraception should be used.

Sexual abstinence

Sexual abstinence is considered a highly effective method only if defined as refraining from heterosexual intercourse during the entire period of risk associated with the study medication. The reliability of sexual abstinence needs to be evaluated in relation to the duration of the study and the preferred and usual lifestyle of the participant.

NOTES:

- a) In case of newly started contraception pills/IUDs, PI should consider the correct timing of starting/applying such methods in relation to the menstrual cycle and the manufacturing instruction as when these newly started methods would become effective.
- b) Typical use failure rates may differ from those when used consistently and correctly. Use should be consistent with local regulations regarding the use of contraceptive methods for participants participating in clinical studies.

Potential drug-drug interactions of medicinal products or medical conditions (eg, gastrointestinal disturbances like diarrhea, vomiting) which could impact the effectiveness of oral contraceptives need to be considered as well. Respective prescribing information of concomitant medications needs to be consulted and guidance (SmPC, local/national or international guidance) on the need of additional contraceptive methods be followed.

Female participants using mycophenolate treatment

As per current EMA recommendations for contraception for men and women during mycophenolate treatment (EMA/828208/2017) patients who can get pregnant must use at least

one reliable form of contraception before, during, and for 6 weeks after stopping treatment. Two forms of contraception are preferred.

As per current FDA label information (Cellcept [package insert] 2019), females of reproductive potential taking mycophenolate must receive contraceptive counseling and use acceptable contraception. Patients must use acceptable birth control during the entire mycophenolate therapy, and for 6 weeks after stopping mycophenolate, unless the patient chooses abstinence.

Unless patients are abstinent, acceptable contraceptive methods for females of reproductive potential during, and for 6 weeks after, treatment with mycophenolate are shown below (Cellcept [package insert] 2019, Table 7):

Option 1 Methods to use alone	Intrauterine devices (IUDs) Tubal sterilization Patient's partner vasectomy
-------------------------------------	---

OR

Option 2	Hormone Methods Choose 1		Barrier Methods Choose 1
Choose one hormone method AND one barrier method	Estrogen and progesterone 
• Oral contraceptive pill• Transdermal patch• Vaginal ring Progesterone-only 
• Injection• Implant	AND	Diaphragm with spermicide Cervical cap with spermicide Contraceptive sponge Male condom Female condom

OR

Option 3	Barrier Methods choose 1		Barrier Methods choose 1
Choose one barrier method from each column (must choose two methods)	Diaphragm with spermicide Cervical cap with spermicide Contraceptive sponge	AND	Male condom Female condom

Pregnancy testing

- Women of childbearing potential should only be included after a confirmed menstrual period and a negative highly sensitive serum pregnancy test.
- Additional urine pregnancy testing should be performed at monthly intervals during the treatment period and at End of Treatment/End of Study, after the final dose of study medication and as required locally.

- Pregnancy testing will be performed when pregnancy is suspected
- Pregnancy testing will be performed at Screening and at every post-Screening visit before study medication application.
- If a study participant is pregnant and stays in the study for observation no pregnancy testing will be performed as long as the pregnancy lasts.

Male participants with partners who become pregnant

- The Investigator will attempt to collect pregnancy information on any male participant's female partner who becomes pregnant while the male participant is in this study. This applies only to male participants who receive study medication. If the study participant is later found to be on placebo, then pregnancy data collection can stop.
- After obtaining the necessary signed informed consent from the pregnant female partner directly, the Investigator will record pregnancy information on the appropriate form and submit it to the Sponsor within 1 working day of learning of the partner's pregnancy. The female partner will also be followed to determine the outcome of the pregnancy. Information on the status of the mother and child will be forwarded to the Sponsor. Generally, the follow-up will be at least 12 months after the delivery date. Any termination of the pregnancy will be reported regardless of fetal status (presence or absence of anomalies) or indication for the procedure.

Female Participants who become pregnant

- Any female participant who becomes pregnant while participating in the study will discontinue study medication.
- The Investigator will collect pregnancy information on any female participant who becomes pregnant while participating in this study. Information will be recorded on the appropriate form and submitted to the Sponsor within 1 working day of learning of a participant's pregnancy. The participant will be followed to determine the outcome of the pregnancy. The Investigator will collect follow-up information on the participant and the neonate and the information will be forwarded to the Sponsor. Generally, the follow-up will be at least 12 months after the delivery date. Any termination of pregnancy will be reported, regardless of fetal status (presence or absence of anomalies) or indication for the procedure.
- While pregnancy itself is not considered to be an AE or SAE, any pregnancy complication or elective termination of a pregnancy will be reported as an AE or SAE. A spontaneous abortion is always considered to be an SAE and will be reported as such. Any post-study pregnancy related SAE considered reasonably related to the study medication by the Investigator will be reported to the Sponsor as described in Section 8.3.5. While the Investigator is not obligated to actively seek this information in former study participants, he or she may learn of an SAE through spontaneous reporting.
- The Investigator should obtain obstetric history of the study participant, outcomes of prior pregnancies, complications of pregnancy and parturition, birth defects and health problems in infancy in earlier offspring and known family history of birth defects.

